## 9.2 Run-in period – 4 weeks (Week -4 to Week -1)

Eligible participants will be contacted to undergo a 4 week (28 days) run-in period, during which they will be consuming the placebo and following an exercise intervention. Participants will come to the clinic to pick up the placebo. Compliance calls will be completed throughout the run-in period at fixed intervals.

Instructions during the run-in period:

1. Begin consuming placebo according to dosing instructions provided
2. Begin exercise regimen according to instructions provided (20 min aerobic exercise/day; 3 days/week) and record exercise in an exercise diary
3. Complete Daily Bowel Habits Diary, 3DFR and subject diary
4. Record adverse events

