## 9.5 Visit 3 (Week 6, 42 ± 3 days)

Participants will return to the clinic fasted for 12 hours, with the unused product, in addition to completed subject diaries, food records, daily bowel habits diaries and exercise diaries, for visit 3. Compliance calls will be made at fixed intervals.

Visit 3 assessments include:

1. Review concomitant therapies and adverse events
2. Collect unused investigational product; calculate compliance
3. Collect and review Subject Diary
4. Collect and review 3DFR
5. Collect and review Daily Bowel Habits Diary
6. Collect and review Exercise Diary
7. Seated resting blood pressure, heart rate, respiratory rate, and temperature measurements
8. Weight (BMI calculation), waist and hip circumference measurements (waist/hip circumference ratio)
9. Dispense investigational product and instruct participants on use
10. Dispense Subject Diary
11. Dispense 3DFR
12. Dispense Daily Bowel Habits Diary

Protocol 20BWHM:

A randomized, double-blind, placebo-controlled study to investigate the effects of a *Bifidobacterium breve* strain on fat loss in healthy adults

13. Dispense Exercise Diary
14. Dispense stool collection kits

The next visit will be scheduled for week 12 (EOS).

Reminders for participants prior to their next in-clinic visit:

1. Return to the clinic in a fasted state (12 hours or greater)
2. Maintain exercise intervention (20 min aerobic exercise x 3 days/week)
3. Abide by instructions for prescribed medications as per Section 7.3.1 and OTC medications, supplements, and food/drinks as per Section 7.3.2
4. Limit alcohol intake (<2 standard drinks per day or <10 per week)
5. Complete and return stool collections
6. Complete and return Daily Bowel Habits Diary
7. Complete and return 3DFR
8. Complete and return Exercise Diary
9. Complete and return Subject Diary
10. Return unused IP

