## **9.6 Visit 4 - End of Study (Week 12, 84 ± 3 days)**

Participants will return to the clinic fasted for 12 hours or greater with the unused product, in addition to completed subject diaries, food records, daily bowel habits diaries, exercise diaries, and stool collections, for assessments. Compliance calls will be made at fixed intervals.

Visit 4 assessments include:

1. Review concomitant therapies and adverse events
2. Return the unused investigational product in the original packaging and remnants; calculate compliance
3. Collect and store stool samples
4. Collect and review Subject Diary
5. Collect and review 3DFR
6. Collect and review Daily Bowel Habits Diary
7. Collect and review Exercise Diary
8. Urine collection
  - a. Urinalysis (microscopy, chemical, urobilinogen/urine bilirubin)
9. Seated resting blood pressure, heart rate, respiratory rate, and temperature measurements
10. Weight (BMI calculation), waist and hip circumference measurements (waist/hip circumference ratio)
11. Collect fasted blood samples for analysis of CBC, Na, K, Cl, Fe, Mg, Ca, phosphate, HbA1c, fasting glucose, eGFR, creatinine, BUN, AST, ALT, GGT, ALP, total bilirubin, lipid profile, and fasting insulin
12. DXA scan

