## 17.2 Appendix II: Daily Bowel Habits Diary with Bristol Stool Scale

Daily Bowel Habits Diary with Bristol Stool Scale will be completed every day by the participants.

Date:						
Comments/Therapies/Medication (dose, frequency, reason for use)/Changes in Health:						

For each bowel movement you experienced today record the time (in 24-hour format) for question 1 and circle Yes or No (Y/N) for questions 2-7.
 
For question 5 please refer to the Bristol Stool Scale and record the type that best describes the bowel movement.
 
If you do not have any bowel movements, circle 0 and complete question 2, 6 and 7.
						
	Bowel Movement Number					
	* If required, additional movements and details can be added to the back of the diary					
	0	1	2	3	4	5
1. Time of Bowel Movement (hh:mm)	N/A	____ : ____	____ : ____	____ : ____	____ : ____	____ : ____
2. Straining to start defecation?	Y / N or N/A	Y / N	Y / N	Y / N	Y / N	Y / N
3. Straining to stop defecation?	N/A	Y / N	Y / N	Y / N	Y / N	Y / N
4. Feeling of incomplete defecation?	N/A	Y / N	Y / N	Y / N	Y / N	Y / N
5. Bristol Stool Form Type (1-7) see below?	N/A					
6. Were laxatives, enemas or suppositories used in the 24 hours prior to the bowel movement?	Y / N	Y / N	Y / N	Y / N	Y / N	Y / N
7. For Females: Do you feel that your bowel movements today were affected by your menstrual cycle? Y / N						

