6. The difference in change from baseline between B. breve and placebo in the frequency of bowel movements after 6 and 12 weeks of supplementation	
H06.1:
 
There is no difference in mean change in the frequency of bowel movements from baseline at week 6 between B. breve and placebo
 
H06.2:
 
There is no difference in mean change in the frequency of bowel movements from baseline at week 12 between B. breve and placebo

Summary statistics including number of participants, mean, median, standard deviation, minimum, and maximum will be obtained for each visit. Similar summary statistics will be obtained for each available change from baseline to each subsequent visit. Mean values will be displayed as graphs, with a separate line for each product, and error bars indicating  $\pm$  SEM. Mean changes from baseline will also be graphed similarly.

Continuous secondary outcomes #2 and # 6 will be assessed using linear mixed effects ANCOVA, the fixed effects will include the baseline measurements as covariate and group\*visit as the factor variables. The dependent variable will be the change at each visit.

Continuous secondary outcomes #1, #3, #4, and #5 will be assessed using ANCOVA, with the baseline measurements as covariate and group as the factor variable. The dependent variable will be the change from baseline at week 12.

Q-Q plots and residuals versus fitted values plots will be generated for the evaluation of the model adequacy. If the residual plots show violation of the model assumptions, log or other transformation of the dependent variable will be performed.

Between group differences will be assessed by two-sample t- test. If the outcome is not normally distributed, then Wilcoxon rank sum test will be used.

Within group differences will be assessed by paired t-test if the outcome is normally distributed and Wilcoxon signed rank test otherwise. P-values and 95% confidence intervals will be calculated.

For categorical variables, counts and percentages will be presented. The denominator for each percentage will be the number of subjects within the study group for that visit/week unless otherwise specified. Possible differences between groups will be assessed by using the two-tailed Chi-squared or Fisher's exact test, as appropriate.

The frequency of BMs will be calculated as the average number of BMs per day over the 7 days prior to baseline and 7 days prior to week 6 and week 12.

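### Bowel movement frequency is baseline-adjusted on 7 diary days only, although the 28-day run-in diary could supply a steadier covariate at almost no cost

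*SAP*

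**What the plan says.** SAP 5.2 and protocol 12.3 agree on the derivation. Frequency is a daily average: "The frequency of BMs will be calculated as the average number of BMs per day over the 7 days prior to baseline", and likewise "7 days prior to week 6 and week 12". Outcome 6 carries two hypotheses, H06.1 (week 6) and H06.2 (week 12). It is analysed by a linear mixed-effects ANCOVA of the change at each visit, with group, visit and their interaction, and the baseline value as covariate.

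The diary covers far more days than these windows. Protocol Appendix II (17.2) says "Daily Bowel Habits Diary with Bristol Stool Scale will be completed every day by the participants". Protocol 9.2 sets the run-in length, "Eligible participants will be contacted to undergo a 4 week (28 days) run-in period", and tells participants during it to "Complete Daily Bowel Habits Diary, 3DFR and subject diary". The Schedule of Assessments (1.3) has the diary handed out at screening and returned at baseline, week 6 and week 12. Randomisation takes place at the baseline visit, so every run-in day precedes it.

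Neither document gives a reason for 7 days, and neither gives a variance for bowel movement frequency.

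**The concern.** A 7-day mean carries day-to-day noise. When it is the only baseline covariate, that noise weakens its relation to the follow-up value, and between-person variation that could have been removed stays in the residual. Three more weeks of daily records on the same participants, made before allocation, are collected and not used in this model.

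What is at stake is the width of the interval for outcome 6. The trial is sized only on fat (protocol 12.1), so precision for this outcome is whatever the analysis can extract from about 40 completers per arm.

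**Working it through.** **Step 1. Check of the multiplier.** Protocol 12.1 assumes 40 completers per arm, 80% power and a two-sided 5% level. With multiplier 2.84 (t-based, 78 df), the detectable difference is 2.84 × SD × √(2/40).
- Percent fat: 2.84 × 1.19 × 0.2236 = 0.756, stated as 0.76.
- Fat mass: 2.84 × 1.24 × 0.2236 = 0.787, stated as 0.79.

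The primary figures reproduce. The same multiplier and 40 per arm are used below. The plan has no corresponding figure for bowel movements.

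**Step 2. Assumed inputs (none are in the documents).**
- Between-person variance τ²: 0.16 to 0.25 (SD 0.4 to 0.5 BM/day)
- Daily variance v: 0.3 to 1.2, days independent
- Variance of true individual change c: 0.02 to 0.20
- Middle case: τ² = 0.25, v = 0.6, c = 0.06

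**Step 3. Residual variance at one visit.** With a 7-day follow-up mean and a baseline covariate whose noise variance is n:

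R = τ² + c + v/7 − τ⁴/(τ² + n)

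The 7-day baseline is itself a covariate, so modelling the change or the follow-up value gives the same group contrast and the same R.

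**Step 4. Stable run-in.** The 7-day baseline alone has n = v/7. With the run-in mean added, n = v/28, because under a stable run-in the 28-day mean already contains all the information in the 7-day mean.

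Middle case:
- 7 days: R = 0.3957 − 0.0625/0.3357 = 0.2095. Detectable difference 2.84 × √(2 × 0.2095/40) = 0.29 BM/day.
- Run-in mean added: R = 0.3957 − 0.0625/0.2714 = 0.1655. Detectable difference 0.26 BM/day.
- Cut in variance: 1 − 0.1655/0.2095 = 21%.

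Extremes of the grid:
- Smallest gain (τ² = 0.16, v = 0.3, c = 0.20): 0.2767 to 0.2529, a cut of 9%.
- Largest gain (τ² = 0.25, v = 0.3, c = 0.02): 0.0994 to 0.0731, a cut of 26%.

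**Step 5. Unstable run-in.** Let each person's first 21 days be shifted by an amount that varies between people with variance s. With both covariates in the model, the precisions of the last 7 and the first 21 days add:

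1/n = 7/v + 1/(s + v/21)

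Middle case:
- s = 0.06: 1/n = 11.67 + 11.29, so n = 0.0436 and R = 0.1828. Cut 13%, detectable difference 0.27.
- s = 0.20: 1/n = 11.67 + 4.375, so n = 0.0623 and R = 0.1956. Cut 7%, detectable difference 0.28.

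For s from 0.02 to 0.20 over the whole grid, the cut runs from about 2% (τ² = 0.16, v = 0.3, c = 0.20, s = 0.20: 0.2767 to 0.2721) to about 21% (τ² = 0.25, v = 0.6, c = 0.02, s = 0.02: 0.1695 to 0.1333).

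**Step 6. Why both covariates.** If the 28-day mean replaced the 7-day baseline, then n = (21/28)² × s + v/28. In the middle case with s = 0.20, n = 0.1125 + 0.0214 = 0.1339 and R = 0.3957 − 0.0625/0.3839 = 0.2329, which is 11% worse than the present plan. With both in the model this loss cannot arise in R.

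**Step 7. Autocorrelated days.** Replace v/L by (v/L) × [1 + 2 Σ (1 − k/L) ρᵏ], summed over k = 1 to L − 1. For a stable run-in the cut over the grid is about 9% to 26% at ρ = 0.2 and about 8% to 25% at ρ = 0.4.

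**The case against.** The strongest defence is that the 7-day rule is prespecified, identical in both documents and matched to outcomes defined after 6 and 12 weeks. A week ending at the visit covers each weekday once. This stands, and it is why the outcome windows should stay.

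It can also be said that the run-in is not one steady state. Participants begin exercise and placebo at its start (protocol 9.2). Users of probiotics or prebiotics stop them 30 days before baseline (protocol 7.3.2), only two days before a 28-day run-in begins. The protocol's introduction also links exercise to digestion and the microbiota. This stands too, and it shrinks the gain (Step 5). It does not create bias: a pre-randomisation covariate is unrelated to allocation however unstable it is.

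Three stronger readings are tempting, and the documents do not support them.
- **That the plan throws away about four fifths of the data.** The windows use 21 of 28 + 84 = 112 run-in and treatment days. That is a share of days, not of information, and most of the unused treatment days lie away from the named time points.
- **That menstrual-cycle noise spoils the outcome.** The diary does ask women "Do you feel that your bowel movements today were affected by your menstrual cycle", and no analysis uses the answer. But the share of menstruating participants is not given, and men, post-menopausal women and women after hysterectomy are eligible. Any effect would be variance, not bias. For an assumed 28-day cycle, week 12 falls 84/28 = 3.0 cycles after baseline, so phase tends to cancel there; only week 6 (1.5 cycles) is out of phase.
- **That follow-up should be redefined as 28-day means.** In the middle case this would take the detectable difference to 0.20 BM/day. But it estimates an average over weeks 3 to 6 and 9 to 12, and it would dilute an effect that builds up over time.

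**Conclusion.** The point holds as a modest loss of precision in one secondary outcome. It is not an error, a contradiction or a source of bias, and the primary endpoint and the sample size are unaffected.

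With a stable run-in, the added covariate cuts residual variance by about 9% to 26%. Since 1 − √(1 − 0.086) = 4% and 1 − √(1 − 0.26) = 14%, the detectable difference falls by about 4% to 14%. If the early run-in is a transition the variance cut is about 2% to 21%, depending on how much people differ in it.

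All of these figures rest on assumed variances and on a single-visit formula standing in for the mixed model. The gain is smallest where true individual change is large. The direction does not depend on the particular values: with the 7-day baseline kept in the model, a further pre-randomisation measure of the same quantity cannot raise the residual variance, and it costs one degree of freedom.

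**What to change.** In SAP 5.2 and protocol 12.3, before unblinding:
1. Keep the 7-day windows at baseline, week 6 and week 12 as the definition of frequency and of its change.
2. Define a second baseline variable: mean bowel movements per day over all recorded run-in diary days before randomisation (up to 28).
3. Enter it in the mixed ANCOVA for outcome 6 alongside the 7-day baseline, not in its place.
4. If wanted, report means over the last 28 days before week 6 and week 12 as a sensitivity analysis only, labelled as a different quantity.

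The cost is a few lines of SAP and protocol wording, some derivation code and one extra covariate. No new data, visits or participant burden are involved.

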### **5.3 Exploratory Outcomes**

Exploratory Outcomes	Hypothesis
9. Total body fat (%) change during the run-in period as assessed by BIA	H09.1: There is no difference in mean change in total body fat (%) during the run-in period as assessed by BIA between B. breve and placebo

10. Comparison of total body fat (%) as assessed by BIA and DXA at baseline	H010.1: There is no difference in mean in total body fat (%) as assessed by BIA and DXA at baseline between B. breve and placebo
---	---

Exploratory outcomes differences will be assessed by two-sample t- test. If the outcome is not normally distributed, then Wilcoxon rank sum test will be used.

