### Exploratory analyses

1. Total body fat (%) change during the run-in period as assessed by bioelectrical impedance analysis (BIA)
2. Comparison of total body fat (%) as assessed by BIA and DXA at baseline

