**8.6 Randomization**

A randomization schedule will be created and provided to the Investigator indicating the order of randomization. Each participant will be assigned a randomization code according to the order of the randomization list generated using [www.randomization.com](http://www.randomization.com). Enrolled participants will be randomized to the different study arms at Day 0.

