## 9.4 Baseline (Visit 2, Week 0)

Eligible participants (compliant with the exercise intervention and placebo consumption during the run-in period) will return to the clinic fasted for 12 hours with completed subject diaries, food records, daily bowel habit diaries, exercise diaries, and stool collections, for baseline assessments. Compliance calls will be made at fixed intervals (bi-weekly). Participants who have not provided a stool sample within 3 days of visit 2 and participants who have significant weight loss (> 0.7 kg/week) during the run-in period will be withdrawn from the study.

Baseline (Day 0) assessments include:

1. Review concomitant therapies and adverse events
2. Assess inclusion and exclusion criteria
3. Collect remaining placebo and calculate compliance
4. Physical examination
5. Collect and store stool samples
6. Collect and review Daily Bowel Habits Diary
7. Collect and review 3DFR
8. Collect and review Exercise Diary
9. Collect and review Subject Diary
10. Urine collection
  - a. Urine pregnancy test for female participants that are of child-bearing potential
  - b. Urinalysis (microscopy, chemical, urobilinogen/urine bilirubin)
11. Seated resting blood pressure, heart rate, respiratory rate, and temperature measurements
12. Weight (BMI calculation), waist and hip circumference measurements (waist/hip circumference ratio)

13. Randomization of eligible participants
14. Body fat composition as determined by BIA
15. DXA scan
16. Collect fasted blood samples for analysis of CBC, Na, K, Cl, Fe, Mg, Ca, phosphate, HbA1c, fasting glucose, eGFR, creatinine, BUN, AST, ALT, GGT, ALP, total bilirubin, lipid profile, and fasting insulin
17. Dispense investigational product and instruct participants on use
18. Dispense Daily Bowel Habits Diary
19. Dispense 3DFR
20. Dispense Exercise Diary
21. Dispense Subject Diary

The next visit will be scheduled for week 6.

Reminders for participants prior to their next in-clinic visit:

1. Return to the clinic in a fasted state (12 hours or greater)
2. Maintain exercise intervention (20 min aerobic exercise x 3 days/week)
3. Abide by instructions for prescribed medications as per Section 7.3.1 and OTC medications, supplements, and food/drinks as per Section 7.3.2
4. Limit alcohol intake (<2 standard drinks per day or <10 per week)
5. Complete and return Daily Bowel Habits Diary
6. Complete and return 3DFR Diary
7. Complete and return Exercise Diary
8. Complete and return Subject Diary
9. Return unused IP

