### 2.3 Exploratory analyses

1. Total body fat (%) change during the run-in period as assessed by bioelectrical impedance analysis (BIA)
2. Comparison of total body fat (%) as assessed by BIA and DXA at baseline

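### SAP 5.3 tests both exploratory body-fat outcomes between arms before any B. breve is taken, so neither test answers the question listed

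*SAP*

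**What the plan says.** Protocol section 5 and SAP 2.3 list the same two exploratory analyses. The first is the change in BIA percent body fat over the run-in. The second is a "Comparison of total body fat (%) as assessed by BIA and DXA at baseline". Neither mentions the study arms.

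SAP 5.3 turns both into arm contrasts. H09.1 is that there is "no difference in mean change in total body fat (%) during the run-in period as assessed by BIA between B. breve and placebo". H010.1 reads: "There is no difference in mean in total body fat (%) as assessed by BIA and DXA at baseline between B. breve and placebo". The method for both is one sentence, "Exploratory outcomes differences will be assessed by two-sample t- test", with the Wilcoxon rank sum test as the fallback.

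The timeline is in the Protocol:

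- Section 9.2: all participants undergo the run-in, "during which they will be consuming the placebo and following an exercise intervention". Section 8.4 also gives placebo only for this period.
- Section 8.6: "Enrolled participants will be randomized to the different study arms at Day 0".
- Section 10.7: BIA is done at screening and baseline only. Section 10.8: the first DXA is at Visit 2.
- Section 9.4: BIA and DXA are items 14 and 15 at Visit 2; dispensing of the investigational product is item 17.

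**The concern.** Every measurement behind these two outcomes is taken before anyone has had B. breve. A comparison of the future arms on such data checks the randomisation. It does not show whether body fat moved during the run-in or how far BIA differs from DXA.

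The risk is misreading. A non-significant H09.1 could be reported as no change during the run-in, and a non-significant H010.1 as agreement between the devices. A significant result on an arm contrast could be taken as meaningful when it is chance or, in a set depleted by dropout, selection. If both tests were independent arm contrasts, the chance of at least one false positive would be 1 - 0.95² = 9.75%.

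The size of the device difference is of some interest here. The body-fat entry limits in Protocol 7.1 are 5 points lower by BIA than by DXA in both sexes (25% and 30% for women, 15% and 20% for men), and the documents give no reason.

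**Working it through.** **The plan's own calculation.** The only design figure is for the primary outcome (Protocol 12.1): 40 completers per arm, SD 1.19 points, detectable difference 0.76 points. With a t-test on 78 degrees of freedom the detectable difference at 80% power is 0.755 points, and power at 0.76 is 80.5%. The figure reproduces and is not in question. No precision or power is stated for the exploratory outcomes.

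**H09.1.** Write each participant's run-in change as μ + error. Arms are assigned after the run-in and all took placebo, so the expected arm difference is μ - μ = 0 for any μ. Simulation with 20,000 runs, 50 per arm and SD 1.19 (the 12-week figure, borrowed as an assumption) gives:

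| True run-in change (points) | Planned two-sample test rejects | Pooled paired test (n = 100) rejects |
|---|---|---|
| 0 | 4.9% | 5.3% |
| -0.5 | 5.1% | 98.5% |
| -1 | 5.0% | 100% |
| -2 | 4.8% | 100% |

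The same data analysed as a pooled paired change:

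- 95% half-width = t(99) × SD/√100 = 1.984 × 1.19/10 = 0.24 points. For SD 0.6 to 2.4 it is 0.12 to 0.48.
- Detectable change at 80% power = 0.283 × 1.19 = 0.34 points. For SD 0.6 to 2.4 it is 0.17 to 0.68.
- Testing each arm separately (n = 50): 0.404 × 1.19 = 0.48 points.

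**H010.1.** The sentence can be read in three ways.

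1. *Arm contrast of BIA minus DXA.* An offset b common to both arms cancels: b - b = 0. With assumed between-person SD 5 to 7 points and correlation 0.7 to 0.95, rejection stays at 4.8% to 5.3% for offsets of 0, 2 and 5 points.
2. *Separate arm contrasts of BIA and of DXA.* These are two baseline balance tests. Neither involves the difference between devices.
3. *Unpaired test of BIA against DXA.* This addresses the right difference but ignores that both values come from one person. Under the same assumptions it rejects 0% to 0.06% of the time at zero offset, far below the nominal 5%. At an offset of 2 points it rejects 54% to 100% of the time, against 95.5% to 100% for the paired test.

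Precision under reading 3, 100 values per device: half-width = t(198) × SD × √(2/100). This is 1.972 × 5 × 0.1414 = 1.39 points at SD 5 and 2.23 at SD 8. Paired: 1.984 × SD of the difference/10, which is 0.40 at SD 2 and 0.79 at SD 4. The unpaired interval is therefore about 1.8 times (1.394/0.794) to 5.6 times (2.231/0.397) as wide. The documents give none of these BIA and DXA SDs or correlations; they are assumptions.

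**Whether other text fills the gap.** SAP 5.1, 5.2 and 6.1 each add a within-group paired test. SAP 5.3 does not. Protocol 12.3 has a general within-group paired test, but nothing that covers two devices at one visit.

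**The case against.** The strongest reply concerns the run-in outcome. The general paired-test sentence in Protocol 12.3 is not restricted to named endpoints, and the change formula there allows screening as the reference visit. On that reading a paired run-in test would be done in each arm, both on placebo, and would show whether body fat changed. This has some force: at SD 1.19 the cost would be precision, 0.48 against 0.34 points detectable. But the SAP section written for this outcome does not carry the test over, and the stated null would still be the arm contrast. The reply does not help the device comparison.

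It can also be said that H09.1 is not strictly true in every analysis set. The ITT and PP populations in SAP 3 depend on post-randomisation data, and Protocol 9.4 lists randomisation (item 13) just before BIA and DXA. Both points are correct. Differential loss could separate the arms, but that would be selection and not an effect of B. breve. The order at Visit 2 matters little in a blinded trial with no product yet dispensed.

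Finally, the precision figures rest on borrowed or assumed SDs, the outcomes are exploratory, and baseline arm comparisons are this plan's habit. All true, and they bear on priority. The logical point does not depend on any SD.

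**Conclusion.** The concern holds. As specified, the run-in test rejects at about its nominal 5% whatever the true change, given valid randomisation and no selective loss. The BIA and DXA test either does not estimate the device difference (readings 1 and 2) or does so with an interval about 1.8 to 5.6 times as wide as pairing would give, under the assumed SDs (reading 3).

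The damage is confined to these two exploratory outcomes. The primary analysis, the secondary outcomes and the sample size are unaffected. It should be corrected because the stated tests do not match the stated questions and the correction is cheap.

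**What to change.** Reword SAP 5.3 as follows.

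- **Run-in change.** Report the within-participant BIA change from Visit 1 to Visit 2, pooled over arms, with a 95% confidence interval and a paired t-test or signed rank test. State the analysis set, for example all randomised participants with both BIA values; this is not one of the three populations in SAP 3 and needs its own line. State that the interval runs from week -6/-5 to week 0, so it is longer than the 4-week run-in. Describe the result as an uncontrolled change in those retained, since Protocol 9.4 says "participants who have significant weight loss (> 0.7 kg/week) during the run-in period will be withdrawn from the study".
- **BIA against DXA.** Define the variable as BIA minus DXA percent body fat at Visit 2. Report its mean in all participants with both measures, with a 95% confidence interval, a paired t-test or signed rank test, and Bland-Altman limits of agreement. A split by sex is optional.
- **Arm contrasts.** If kept, label them as baseline balance checks.

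The cost is two reworded hypotheses, a rewritten method sentence, one derived variable and a line on the analysis set. All the data are already scheduled for collection.
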